[figure not shown]

A Proof of Concept Study Evaluating the Role of Emerging
Ultrasound Technologies in the Assessment and Monitoring
of Localised Prostate Cancer in Men on an Active
Surveillance Programme

Study Protocol: Evaluating the Role of Ultrasound in
Prostate Cancer (ERUP)

6th December 2021

Evaluating the Role of Ultrasound in Prostate Cancer Study (ERUP Study)

Full title of the research:

A proof of concept study evaluating the role of emerging ultrasound technologies in the assessment and monitoring of localised prostate cancer in men on an active surveillance programme.

Short title for this project:

Evaluating the role of ultrasound in prostate cancer

Lead researcher

[name]

Consultant Sonographer
Ultrasound, Hull Teaching Hospitals

Research team

[name]

Consultant Urologist
Urology, Hull Teaching Hospitals

[name]
[name]
[name]

Abstract

Research plan, study design and protocol

Summary of the study:

Active surveillance (AS) is becoming an increasingly common treatment option for men who have been diagnosed with localised low-grade prostate cancer (PCa). Low-grade disease is commonly noted by clinicians to be clinically insignificant cancer but remains a psychological burden to many men in this cohort. There is consensus that regular review is required for men on AS so that early treatment can be undertaken if there is disease progression, and to support men living with a cancer diagnosis. Some AS protocols, including NICE, advocate the use of MRI as a regular part of the monitoring pathway. Unfortunately, access to MRI for AS, within the current health care environment in the UK, is limited due to increasing demand for primary diagnostic examinations, particularly in the post Covid-19 recovery phase. Emerging technologies in ultrasound imaging may, however, add another diagnostic tool to monitor disease for patients on AS. This proof of concept study is to evaluate whether new multi-parametric ultrasound techniques can safely reduce the number of MRIs required for effective AS.

Men being investigated for PCa will be invited to undergo an ultrasound examination of their prostate, via the rectum, in addition to the diagnostic MRI undertaken as part of normal care. The findings of the ultrasound will be directly compared with the MRI and any subsequent biopsy samples taken as part of routine care. Those who then progress onto AS will be invited to undergo regular rectal prostate ultrasound examinations. These will be compared with previous imaging for signs of change.

This study will also evaluate the changing role of practitioners who will be using new technologies and making decisions about disease progression. The ability to implement new techniques will be assessed. All imaging will be undertaken at Castle Hill Hospital over a 24-month period from commencement of the study.

Contents

Evaluating the Role of Ultrasound in Prostate Cancer Study (ERUP Study)	i
Full title of the research:.....	i
Short title for this project:	i
Lead researcher.....	i
Research team	i
Abstract	ii
Research plan, study design and protocol.....	ii
Summary of the study:.....	ii
Research Plan	6
1.1 Purpose and design.....	6
1.1.1 Clinical context:.....	6
1.1.2 Technological improvements.....	7
1.1.3 Implementing change	7
1.1.4 Skill mix	8
1.1.5 Normalisation Process Theory (NPT)	8
1.2 Study Aim	8
1.3 Primary and secondary objectives	9
1.3.1 Primary objective	9
1.3.2 Secondary objectives	9
1.4 Study phases	9
1.4.1 Phase 1:.....	9
1.4.2 Phase 2:.....	10
1.4.3 Phase 3:.....	10
1.4.4 Phase 4:.....	10
1.5 Study design and methodology – Phase 1	11
1.5.1 Phase 1: Patient population.....	11
1.5.2 Eligibility criteria in clinical practice.....	11
1.5.3 Phase 1 recruitment.....	11
1.5.4 Sample size – phase 1	11
1.5.5 Inclusion criteria for phase 1.....	12
1.5.6 Exclusion criteria for phase 1	12
1.5.7 Phase 1 recruitment process	13

1.5.8	Ultrasound appointments – phase 1.....	13
1.5.9	Image collection.....	13
1.5.10	Scan protocol.....	13
1.5.11	Data collection - Phase 1.....	15
1.5.12	Data assessment.....	15
1.5.13	Data collation.....	15
1.5.14	Data analysis.....	16
1.6	Study design and methodology – Phase 2.....	16
1.6.1	Phase 2 recruitment.....	16
1.6.2	Sample size phase 2.....	17
1.6.3	Inclusion criteria for phase 2.....	17
1.6.4	Exclusion criteria for phase 2.....	17
1.6.5	Phase 2 recruitment process.....	18
1.6.6	Participation and patient contact.....	18
1.6.7	Image collection Phase 2.....	18
1.6.8	Data collection phase 2.....	18

1.1 Purpose and design

Across the UK prostate cancer is the most common cancer in men. Developments in magnetic resonance imaging (MRI), and the implementation of a targeted biopsy regime, have resulted in a considerable improvement in the detection of prostate cancer. The advent of robotic prostatectomy, and improvements in radiotherapy, have both lessened the post-treatment side effects but no treatment is without significant risk of complications.

1.1.1 Clinical context:

Prostate cancer can be present as an indolent low-grade cellular change to the tissue but with very little risk of this progressing to a metastatic life threatening disease. Despite the improved diagnostic capabilities, there remain a significant proportion of men in whom low-grade cancer is detected and consequent treatment options may present a higher risk to quality of life than the presence of the localised disease. NICE CG 131 (2019) recommends men are offered active surveillance (AS) or watchful waiting (WW) as an option for low-risk localised prostate cancer and for whom radical prostatectomy or radical radiotherapy is suitable should advancing disease be detected. Both AS and WW involve proactively monitoring the patient for signs of disease progression rather than undertaking treatment immediately. Patients on an AS pathway are deemed suitable for intervention and curative treatment should there be signs of disease progression; patients on a WW pathway usually have comorbidities that preclude curative treatment but they may benefit from palliative care if there is evidence of future progression. The Prostate Testing for Cancer and Treatment (ProtecT) (Hamdy et al. 2016) trial was established to gain a better understanding of the effectiveness of treatments, including AS, for prostate cancer. ProtecT (Hamdy et al. 2016) concluded that, at a median of 10 years, prostate cancer specific mortality was low regardless of the treatment assigned and that adopting an AS approach is reasonable to avoid life limiting side effects (Da Silva et al. 2017, Klotz et al. 2015).

However, despite the findings of the ProtecT trial (Hamdy et al. 2016) and the NICE guidance 131 (NICE 2019) there is currently no standard approach to AS due to the inequalities in capacity and availability of services in the NHS. It is, however, agreed that men on AS require regular tests which should include a combination of the following:

- Prostate Specific Antigen (PSA)
- digital rectal examinations (DRE)

- MRI scans
- prostate biopsies – either transrectal random or transperineal template biopsy

The improvements in MRI imaging and reporting indicate that regular scans would add valuable information for patients under AS but capacity is significantly hindering this as an available application. An overview of the current clinical pathway for patients in the local region is provided as [appendix 1](#). This highlights the very real impact that capacity issues in MRI has on patient diagnostic pathways.

1.1.2 Technological improvements

However, emerging technologies in ultrasound imaging, which is less hindered by capacity issues within the UK and is utilised, to a degree, in current standard care, may add another diagnostic tool to monitor disease for patients on AS. A multi-parametric ultrasound assessment may provide the crucial diagnostic features that enables ultrasound imaging to be used to monitor disease. A multi-parametric assessment will include standard frequency ultrasound, Doppler ultrasound and high frequency ultrasound imaging. High frequency ultrasound (micro-US) increases the detail of structures imaged, compared to standard trans-rectal ultrasound, and has been demonstrated to be a promising new modality for targeted prostate assessment compared to MRI (Maffei et al. 2019). A recent paper by Matheson et al. (2019) has demonstrated that most men on AS cope well psychologically but the paper is limited in its exploration of what alternative intervention could be made to improve well-being within a AS programme. A crucial question remains as to whether the use of additional imaging and health care intervention could improve patient outcomes.

1.1.3 Implementing change

Traditionally, radiologists or urologists have performed the diagnostic transrectal prostate biopsy procedures within the cancer pathway. In more recent years, skill mix has developed and there is an increasing number of sonographers undertaking these examinations enabling medical capacity to be released. Within the Hull University Teaching Hospitals NHS Trust, the vast majority of prostate biopsies are undertaken by sonographers. Sonographers are trained and qualified to interpret ultrasound imaging. They provide diagnostic reports as part of routine practice. The limitations of traditional US technology used to guide transrectal prostate biopsy precluded any diagnostic assessment during the biopsy procedures; US is used purely to guide where samples will be taken.

1.1.4 Skill mix

The advent of multi-parametric ultrasound may enable a diagnostic assessment of the prostate, both at the initial biopsy and during AS. This will be an additional skill the sonographer will be required to develop. The benefits of skill mix have been documented by various authors, most recently Field and Snaith (2013). However, the impact of role development on sonographers and their radiologist colleagues, which includes changes to roles, responsibilities and accountabilities, has not been previously investigated in any depth. A workforce review by Parker and Harrison (2015) identified that appropriate training in ultrasound is key to providing a safe diagnostic and interventional ultrasound service but what constitutes appropriate training is less well defined.

1.1.5 Normalisation Process Theory (NPT)

Despite the publication of a defined framework for the development and evaluation of research, there remain substantial problems in the design and conduct of studies introducing complex interventions and their subsequent implementation (Finch et al. 2018). The understanding of an implementation processes is key to ensuring that proposed changes to techniques, technologies or interventions are both implemented and sustained in practice; desired outcomes of a 'successful' implementation do include the experiences of those providing the service. If a new technology provides good diagnostic results but is cumbersome and complex to use, it is unlikely to be implemented into routine healthcare practice. A recognised gap exists between developing new treatments and knowledge, and implementing these in practice for the patient who may benefit (De Brún et al. 2016, May, Johnson and Finch 2016). An understanding of the ability to implement the proposed new complex ultrasound techniques in real-life clinical practice will be explored within this proof of concept study. Normalisation process theory (NPT) is the theoretical approach being utilised in this study. NPT is a theory which described the collective work that stakeholders need to engage in to implement interventions in the real world of everyday clinical practice. NPT has 4 components that practitioners need to adopt in order to embed a new process or technology into routine practice. The 4 components: Coherence, Cognitive Participation, Collective Action, and Reflexive Monitoring. These will be explored further in the staff focussed third phase of the study.

1.2 Study Aim

This aim of this proof of concept study is to evaluate if emerging ultrasound technologies can provide reliable and reproducible imaging that can be used to assess the prostate gland in men with known localised prostate cancer and who are being managed with active surveillance.

The impact of additional skill mix for health care practitioners within diagnostic imaging, in the field of prostate cancer assessment and monitoring, will be investigated as a secondary objective of this study. As with many research studies, data is collected in a strict and controlled environment which may not readily translate into a real life clinical setting. The feasibility for implementing changes to the imaging pathways in active surveillance will also be evaluated with the clinical team delivering the current and future service.

1.3 Primary and secondary objectives

1.3.1 Primary objective

The primary objective of the study is to evaluate if emerging multi-parametric ultrasound technologies can provide a viable tool to be used in the active surveillance of men with known localised prostate cancer.

1.3.2 Secondary objectives

Secondary objectives of this study are:

- to evaluate the diagnostic parameters of diagnostic ultrasound that can be utilised to assess disease within the prostate gland.
- To evaluate the diagnostic parameters of diagnostic ultrasound that can be utilised to assess disease progression within the prostate gland.
- To evaluate if the intra and inter operator variability in the assessment of ultrasound imaging parameters of the prostate gland can be investigated.
- To determine if a suitable standardise imaging protocol and reporting tool or model could be utilised in the reporting of transrectal ultrasound imaging of the prostate.
- To gain a better understanding of how new ultrasound technology and techniques can be implemented and embedded into clinical practice.

1.4 Study phases

This study is being undertaken as a PhD research project but within the NHS care setting. The study will consist of four phases:

1.4.1 Phase 1:

In this initial phase, eligible men who have consented to participate will undergo a transrectal ultrasound examination with a standard ultrasound probe and, at the same attendance a transrectal ultrasound examination with a new and novel probe using 29MHz scanning frequency. The images obtained from this examination will be retrospectively compared with the MRI imaging that has been obtained as part of the standard care pathway. The images obtained will be reviewed by two

health care practitioners with experience in prostate imaging and the outcomes of these reviews compared to evaluate agreement levels.

1.4.2 Phase 2:

The second phase of the study will evaluate the use of multiparametric standard and micro ultrasound in the assessment of men who are on an AS or WW pathway. This phase the study will evaluate if there are any changes in the findings at repeat ultrasound examinations that can indicate disease progression. Eligible men, who have consented to participate, will again undergo a transrectal ultrasound examination with a standard ultrasound probe and, at the same attendance a transrectal ultrasound examination with a new and novel probe using 29MHz scanning frequency.

1.4.3 Phase 3:

The process and acceptability of implementing new interventions and technologies into everyday clinical practice is frequently overlooked following research trials. This third phase will explore the views of the health care practitioners, who have consented to participate, regarding the use and implementation of the proposed new technologies; skill mix between these professional groups will be required for successful long term practice. The participants will be recruited from differing professionals within the staff groups of Hull University Teaching Hospitals NHS Trust. An adapted survey tool, derived from normalisation process theory framework, will be used to better understand how and if the new, complex, multi-parametric ultrasound techniques can be implemented within the organisational setting of everyday routine practice. A baseline assessment of confidence in knowledge and skills related to prostate cancer evaluation using ultrasound will be made.

1.4.3.1 Staff training:

Participants in phase 3 will then be provided with training using specific multi-parametric US techniques and will regularly score multi-parametric US examinations. Participants' confidence in knowledge and skills, related to prostate cancer evaluation using US, and how they feel this can be implemented into regular patient care will be assessed, using the same adapted survey at baseline at 6 - 12 months' post implementation.

1.4.4 Phase 4:

A fourth phase of the study is planned. Once outcomes from the initial 3 phases of the study are known the lead researcher intends to organise a national meeting where results will be presented and discussion held between the research team and other centres providing a diagnostic prostate cancer service. The aim of this event is to disseminate results and to obtain a wider understanding of

its acceptance beyond local practice. Multi-parametric ultrasound is novel and there may be resistance to wider implementation. Opportunities and barriers will be explored at this phase 4 event.

The study phases will run concurrently and will be managed by the lead researcher.

1.5 Study design and methodology – Phase 1

1.5.1 Phase 1: Patient population

With consent, all eligible men will be invited to participate in the first phase of the study; [appendix 1](#) outlines the current care pathway and the eligibility criteria utilised in this study. Multi-parametric US will be used to assess the prostate gland prior to the ultrasound guided diagnostic prostate biopsies which is performed as part of routine care. The multi-parametric US examination will be performed blinded to the pre-biopsy MRI undertaken as part of routine care. Multi-parametric US findings will be scored and subsequently correlated to MRI and any related histology findings which are recorded as part of routine care.

1.5.2 Eligibility criteria in clinical practice

MRI is offered to all men who meet the eligibility criteria of age ≤ 75 , PSA ≤ 20 and life expectancy of ≥ 10 years. MRI is reported using the PI-RADS V2 criteria; a 5 point scale with 1 & 2 highly unlikely to have significant prostate cancer, 4 & 5 highly likely to have significant prostate cancer and PI-RADS 3 equivocal and further investigation warranted. The pathway in the Hull University Teaching Hospitals NHS Trust is that patients with PI-RADS score of 1 or 2 are not routinely offered biopsy due to the risk of biopsy complications being greater than the likelihood of prostate cancer. Men meeting these criteria will be invited to participate in phase 1 of the study and the multi-parametric US will be correlated with MRI only. A biopsy will not be performed. Any men from this cohort electing for AS will be invited to join phase 2.

1.5.3 Phase 1 recruitment

Participants for phase 1 of the study will be invited from the cohort of patients referred into Hull Teaching Hospitals with suspected prostate cancer and who meet the criteria for pre prostate biopsy MRI. [Appendix 1](#) outlines the current clinical pathway and participants for the study will be invited from those who fulfil the criteria for pathway A of the local service.

1.5.4 Sample size – phase 1

As this is a proof of concept study testing the technology of ultrasound and with no previous comparable data little is known about the standard deviation and the distribution of US scores. This

makes determining a sample size based on means and variances difficult. Therefore, a sample size estimation is based on a representative proportional of the annual referral rate into this service. The sample size for phase 1 will be a minimum of 30 patients and a maximum of 60 patients. This represents 5% - 10% of the total patient population presenting with suspected prostate cancer and undergoing prostate biopsy in one calendar year. Given the small numbers within this cohort, all eligible participants will be invited to continue onto phase 2 of the study with maximum cohort of 30 being accepted.

1.5.5 Inclusion criteria for phase 1

The recruitment criteria and pathway for the clinical phases of the study are outlined in the flow charts, [appendix 1](#) and [appendix 2](#). These identify when the participants will be invited to participate, when consent will be obtained and the broad outline of the involvement in the study that participants can expect.

Men referred to urology within Hull University Teaching Hospitals NHS Trust with suspected, but undiagnosed, prostate cancer and:

- Are aged equal to 75 or less
- PSA equal to 20 or less
- Have had a clinical assessment and deemed to have a life expectancy of 10 years or more
- Are able to tolerate a rectal ultrasound examination
- Able to provide informed consent to the study
- Have had a multi-parametric MRI performed as part of routine care pathway
- MRI results will not preclude invitation for participation; men with PI-RADS 1 & 2, who would not be offered biopsy under routine care, are also included in the study. This phase 1 US imaging will be an addition examination for this cohort of patients. Consent for the addition imaging is required. Reference is made to the Phase 1 PIS (v2 03.11.21) and phase 1 ICF (v2 03.11.21).

1.5.6 Exclusion criteria for phase 1

- Patients accessing care in Hull University Teaching Hospitals NHS Trust but who are not suspected of having prostate cancer
- Men referred to urology but who do not meet the eligible criteria for MRI as part of the routine care pathway. This includes men who are over 75 and / or have a PSA over 20
- Men who meet eligibility criteria but in whom MRI has not been completed (due to lack of compliance, artefact, contraindications etc)
- Men who are eligible for inclusion but who cannot tolerate rectal ultrasound examinations.

- Men who are unable to consent to the study

1.5.7 Phase 1 recruitment process

Patients are seen in a specific prostate assessment clinic by a urology nurse specialist. A clinical history is taken and from there, referrals for both MRI and ultrasound guided prostate biopsy are made. At this appointment, all patients will be given an information leaflet for the study. The MRI is undertaken within 14 days of referral; the ultrasound guided prostate biopsy can only be performed following the MRI. The MRI can be distorted due to post biopsy haemorrhage in the prostate gland, and, more importantly, the MRI provides crucial information related to suspected areas of pathology in the gland which are targeted during the biopsy procedure. During the time from referral to MRI the patient will be contacted by the lead researcher and invited into the ultrasound study.

1.5.8 Ultrasound appointments – phase 1

A mutually convenient appointment will be made and confirmed with an appointment letter. The phase 1 recruitment pathway is provided in [appendix 2](#). The patient will attend at the agreed date and time and a face to face consultation with the lead researcher will be undertaken to discuss the study and obtain written consent. The lead researcher will be blinded to the results of the MRI or previous studies at this time to minimise undue coercion into the study.

1.5.9 Image collection

Once written consent has been obtained, the patient will be shown to a private changing area, directly adjacent to the ultrasound examination room and asked to change into a hospital gown. The patient will be escorted into the scan room for the procedure to be undertaken. A chaperone will be present with consent of the patient, as per standard clinical practice. A randomly allocated sonographer who has consented to participate in the study will be introduced and verbal consent obtain for the procedure to commence.

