1.5.10 Scan protocol

The patient will be positioned in a left sided-decubitus position or lithotomy position depending upon which is most comfortable for them. Once comfortable an ultrasound probe from a standard ultrasound machine with a scan frequency of 7.5MHz, and about the size of an adult male's index finger, is gently placed into the rectum and the prostate identified. The following images of the prostate will be obtained and saved onto the PACS system

During the ultrasound examination, the prostate gland will be scanned in a longitudinal and transverse plane from the apex to base, including seminal vesicles, and from right lateral border to

assigned to provide the consultation and biopsy as part of the standard care. Findings of the MRI will then be discussed with the patient and the patient's pathway will proceed as normal.

1.5.11 Data collection - Phase 1

Each participant will be given a unique study ID number. All images, cine loops and data for the study will be acquired and stored under this separate study ID. The data will be stored on the Hull Teaching Hospitals password protected picture archive and reporting system (PACS). A password protected database, stored in a password protected network drive of Hull Teaching Hospitals will hold the unique identifier number and will be used to record study data.

The lead researcher will randomly allocate a unique identifier number to two of the participating healthcare professionals. The reviewers will be randomly allocated to reduce bias as far as possible within a small team. Each reviewer will have their own unique identifier number known only to the lead researcher. The identity of the reviewers will be anonymised. The images and cine loops stored for the study will have no patient identifiable data on them. [Appendix 4](#) outlines the image acquisition and review pathway for phase 1 of the study.

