1.5.14 Data analysis

Once the database is complete for each participant, the lead researcher will compare the:

- ultrasound scores
- ultrasound colour Doppler findings
- prostate volume size
- lesion size

The above criteria will be compared between both the standard and micro-US imaging, and then the standard and micro-US with both MRI and histology. An assessment of agreement will be undertaken to evaluate the concordance between the two reviewers of the same images (Ranganathan, Pramesh and Aggarwal 2017). The relationship between these pairs will be evaluated using Bland-Altman plots. Scores from the ultrasound reviews will also be evaluated to determine inter-and intra-operator agreement between the randomly allocated reviewers. The inter-rater reliability, both within and across subgroups of reviewers, will be assessed using the intra-class correlation coefficient or the Cohen weighted kappa test (de Raadt et al. 2021).

1.6 Study design and methodology – Phase 2

Men eligible for AS will be invited to participate in phase 2. A multi-parametric US examination will be undertaken as part of the AS monitoring regime. Men under AS have a prostate serum antigen (PSA) blood test and digital rectal examination every 6 months. A multi-parametric US examination will be undertaken at these appointments to minimise unnecessary health care interactions for the participants. The multi-parametric US examination will be performed blinded to the previous examinations and histology results. The images will be scored and then correlated with previous imaging scores and current PSA levels. Any changes will be indicated to the lead urologist and the patients will be offered MRI imaging to evaluate any changes using existing gold standard imaging.

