1.10.1.2 Burden

The burden upon the patient is to have two probes separately inserted into the rectum as opposed to once for standard care. The examination time will be extended by a maximum of 10 minutes. The burden is greater for participants with MRI PI-RADS score of 1 or 2. Rectal ultrasound and biopsy is not indicated as part of their standard care pathway and, as such, participation in the study will include a transrectal ultrasound examination that they would not normally receive. Both examinations will take no more than 10 minutes in total and will be planned around clinic attendances to avoid unnecessary visits to the hospital.

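### The planned agreement statistics measure reader agreement on one shared recording, so they cannot be labelled inter-operator agreement or support a claim of reproducible imaging

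*Protocol*

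**What the plan says.** **Aim and objective.** Protocol 1.2 sets out to "evaluate if emerging ultrasound technologies can provide reliable and reproducible imaging". One secondary objective in 1.3.2 is to see whether "intra and inter operator variability in the assessment of ultrasound imaging parameters of the prostate gland" can be investigated.

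**Acquisition.** Under 1.4.1 each man has a "transrectal ultrasound examination with a standard ultrasound probe and, at the same attendance a transrectal ultrasound examination with a new and novel probe". Section 1.5.9 assigns the scanning to one person: "A randomly allocated sonographer who has consented to participate in the study will be introduced". Section 1.10.1.2 counts the insertions: "The burden upon the patient is to have two probes separately inserted into the rectum as opposed to once for standard care".

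**Reading.** Section 1.5.11 states: "The lead researcher will randomly allocate a unique identifier number to two of the participating healthcare professionals". Under 1.5.12 these reviewers score the saved images and loops afterwards at a workstation.

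**Analysis.** Section 1.5.14 compares the two reviewers on one set of images. It then uses the review scores to "determine inter-and intra-operator agreement between the randomly allocated reviewers", and names the intra-class correlation coefficient (ICC) or weighted kappa for inter-rater reliability.

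**Phase 2.** Sections 1.6.7 and 1.6.8 carry over the image collection and the two-reviewer scoring. Section 1.6.10 repeats the statement on operator agreement, takes the phase 1 recording as each man's baseline, and has any score change passed to the consultant urologist.

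**The concern.** The score given to a transrectal scan depends on the man, on how the scan was acquired (probe handling, planes, Doppler settings, which images were stored) and on who reads it. Two readers of one recording differ only in the last of these. Whatever the sonographer did well or badly is present in both scores and makes them agree.

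A high ICC or kappa would therefore show that staff read a given recording alike. It would not show that a second sonographer scanning the same man would produce a recording leading to the same score. Reported as inter-operator agreement, it would lend support to the aim in 1.2 that the design does not provide.

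This matters within the study as well. In phase 2 the sonographer is again randomly allocated and may differ from the one at baseline, so operator differences enter the change scores as noise that nothing in the plan measures.

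**Working it through.** **1. Is there a second acquisition anywhere?** Section 1.4.1 gives one examination per probe type, 1.5.9 gives one sonographer, 1.10.1.2 counts two insertions (one per probe), and 1.5.14 pairs two readings of one image set. Together these fit only one acquisition per probe per attendance. Phase 2 scans are repeat acquisitions, but they are about six months apart, so operator differences are mixed with real change and cannot serve as reproducibility data.

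**2. Is there a figure in the plan to reproduce?** No. The protocol gives no target ICC or kappa, no precision and no variance. The phase 1 size of 30 to 60 is set as a share of annual patients (1.5.4), not from an agreement target.

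**3. What each design estimates.** Let M be the variance between men, O the acquisition (operator) variance, and R the reader variance including residual error.

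- Planned design (one recording, two readers): ICC = (M + O) / (M + O + R).
- Repeat scan by another operator, read by another reader: ICC = M / (M + O + R).
- Difference: O / (M + O + R), the acquisition share of total variance.

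**4. Illustration.** M = 1.0, R = 0.3 and O = 0.1 to 0.5 are assumptions; none comes from the protocol.

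| O | Planned ICC | Repeat-scan ICC | Gap |
|---|---|---|---|
| 0.1 | 1.1/1.4 = 0.79 | 1.0/1.4 = 0.71 | 0.1/1.4 = 0.07 |
| 0.3 | 1.3/1.6 = 0.81 | 1.0/1.6 = 0.625 | 0.3/1.6 = 0.19 |
| 0.5 | 1.5/1.8 = 0.83 | 1.0/1.8 = 0.56 | 0.5/1.8 = 0.28 |

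The gaps are computed before rounding. As O rises, the planned ICC goes up while the repeat-scan ICC goes down.

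**5. Does sample size help?** A simulation (2,000 runs) took total variance 1, reader share 0.20 and acquisition share 0.20. The mean ICC was 0.79 for the planned design against 0.59 for two operators, at both n = 30 and n = 60. At n = 60 the 95% sampling ranges were 0.68 to 0.87 and 0.40 to 0.74. Quadratic weighted kappa on a 5-point score averaged 0.74 against 0.54. More men narrow the ranges but leave the gap.

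**6. Phase 2 change scores.** For an unchanged man scanned independently at two visits, the variance of the score difference contains 2 × O in addition to the reader part. Two-reader agreement within a visit says nothing about that term.

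**The case against.** **Operator may simply mean reader.** Section 1.5.14 ties the word to the reviewers and goes on to speak of inter-rater reliability. The objective in 1.3.2 concerns variability in the assessment, and asks only whether it can be investigated. This stands to a large degree: the ICC or kappa is sound as a reader statistic, and no section expressly promises to measure acquisition variability. But 1.9.3 separates performing the scan from scoring saved images, and the aim in 1.2 is about imaging. On the lenient reading the label and the inference to the aim still fail.

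**One acquisition is a reasonable choice.** A second acquisition would add rectal probe insertions to a burden already acknowledged in 1.10.1.2, in a proof-of-concept study. This stands, and no second acquisition is asked for here. Random allocation also means that sonographer differences in phase 2 act as noise rather than a systematic bias.

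**The text is incomplete.** In the text available, 1.5.10 breaks off and the charts in Appendices 4 and 5 are not reproduced. The sections compared above nevertheless agree with one another.

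A reader might also infer from Appendices 6 and 7, which show a reviewer number but no field for the sonographer, that operator differences can never be recovered. The documents do not support that. The forms as reproduced are evidently partial, since they lack the 5-point and Doppler scales that 1.5.12 places there. They carry the scan date, and 1.5.11 describes a separate study database. Nothing shows that the scanning sonographer goes unrecorded.

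**Conclusion.** The point holds as one of labelling and inference. The planned statistics measure inter-reader agreement on stored images. They contain no acquisition component and cannot by themselves support reproducible imaging.

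The planned ICC is too high, as a measure of scan reproducibility, by the acquisition share of total variance. The direction is certain if acquisition variance is above zero. The size is unknown, and the gap of 0.07 to 0.28 is an illustration under assumed variances, not an estimate for this study. The conclusion also assumes that no second acquisition is planned in the text that is not reproduced.

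It might be inferred that a random operator effect in the analysis would recover the missing component. It would not: with one sonographer per man per attendance it picks up only average differences between sonographers, imprecisely with 30 to 60 men, while acquisition error specific to a man's scan stays confounded with the man. Nor do the documents support keeping one sonographer per man in phase 2, which conflicts with the random allocation in 1.5.9 and strains the blinding to earlier examinations required in 1.6.

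**What to change.** - In 1.3.2, 1.5.14 and 1.6.10, replace inter-operator agreement with inter-reader agreement on stored images.
- Under 1.2, limit the conclusion to reproducible interpretation and state that reproducibility of acquisition is not assessed.
- Make sure the study database in 1.5.11 holds the scanning sonographer's code for every examination in both phases.
- In 1.6.10, report phase 2 score changes descriptively by whether the sonographer was the same as at baseline or different.

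The cost is wording, one data field if it is not already held, one descriptive table, and a narrower reproducibility claim. Participants have no extra examination.
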